1.2.4 Clinical Safety

For nivolumab monotherapy, the safety profile is similar across tumor types (investigator brochure v 2015). The only exception is pulmonary inflammation adverse events (AEs), which may be numerically greater in subjects with NSCLC, because in some cases, it can be difficult to distinguish between nivolumab-related and unrelated causes of pulmonary symptoms and radiographic changes. There is no pattern in the incidence, severity, or causality of AEs to nivolumab dose level. Safety data for subjects with previously treated advanced or metastatic NSCLC treated with nivolumab monotherapy in CA209017 (131 subjects), CA209057 (287 subjects), and CA209063 (117 subjects) were pooled and safety analyses were performed for these pooled subjects who receiving nivolumab monotherapy (a total of 535 subjects)(investigator brochure v 2015). Based on the pooled analyses, nivolumab monotherapy at a dose of 3 mg/kg administered IV Q2W has an acceptable safety profile, as demonstrated by the frequency, severity, and types of AEs, drug-related deaths, SAEs, and AEs leading to discontinuation. The most common adverse events were fatigue (19.6%), decreased appetite (12.3%), nausea (12.0%), and asthenia (10.5%). The majority of drug-related AEs were of Grade 1-2 in severity.

The toxicity profile of ipilimumab at the dose of 3mg/Kg for 4 doses in previously treated patients with metastatic melanoma was assessed in phase 3 trial. One hundred and thirty one patients with received ipilimumab as monotherapy, 380 received it with gp100 peptide, and 132 received gp100 peptide vaccine alone. Patients in the study received a median of 4 doses. Ipilimumab was discontinued

NU Study Number: NU 16N03
BMS Study Number: CA 209-802

for adverse events in 10% of patients. The most common adverse events in patients who received ipilimumab at 3mg/Kg were fatigue (31%), pruritus (23%) and rash (22%)(package insert v 2013). The majority of drug-related AEs were of Grade 1-2 in severity.

In several ongoing clinical trials, the safety of nivolumab in combination with ipilimumab is being explored. Most studies are ongoing and, as such, the safety profile of nivolumab combinations continues to evolve. The most advanced combination under development is nivolumab + ipilimumab in subjects with melanoma. Thus far, the combination of both agents results in a safety profile with similar types of AEs as either agent alone, but in some cases with a greater frequency.³²

Safety data for subjects with previously untreated unresectable or metastatic melanoma treated with nivolumab in combination with ipilimumab in phase III (313 subjects) and phase II (94 subjects) trials were pooled and safety analyses were performed for these pooled subjects receiving nivolumab in combination with ipilimumab (a total of 407 subjects) as described in the investigator brochure BMS-936558/MDX1106 Version No14, 30-Jun-2015.^{22,38} Based on the pooled analyses, nivolumab 1 mg/kg combined with ipilimumab 3 mg/kg administered IV Q3W for 4 doses followed by nivolumab 3 mg/kg IV Q2W has an acceptable safety profile, as demonstrated by the frequency, severity, and types of AEs, drug-related deaths, SAEs, and AEs leading to discontinuation. The most frequently reported drug-related AEs of any grade were diarrhea (43.0%), fatigue (35.4%), pruritus (33.4%), rash (31.0%), nausea (24.8%), pyrexia (18.7%), ALT increased (18.2%), AST increased (16.7%) and decreased appetite (16.2%). The most frequently reported drug-related Grade 3-4 AEs ($\geq 5\%$ of subjects) were colitis (9.6%), diarrhea (8.80%), ALT increased (8.4%), lipase increased (8.4%), and AST increased (5.9%). Study drug toxicity was considered responsible for 2 deaths; 1 subject died of ventricular arrhythmia within 30 days of the last dose and the other died of pneumonitis between 31 and 100 days of the last dose.

Most recently, nivolumab at 3mg/Kg every 2 weeks combined with ipilimumab at 1mg/Kg every 6 weeks was administered in patients with advanced NSCLC in the first line setting (CheckMate 012 trial).²³ In this trial 4 different combinations of nivolumab were compared (nivolumab 1mg/Kg every 3 weeks x 4+ ipilimumab 1mg/Kg every 3 weeks x 4 followed nivolumab 3mg/Kg every 2 weeks (N=31), nivolumab 1mg/Kg every 2 weeks + ipilimumab 1mg/kg every 6 weeks (N=40), nivolumab 3mg/Kg every 2 weeks + ipilimumab 1mg/Kg every 12 weeks (n=38) and finally nivolumab 3mg/Kg every 2 weeks combined with ipilimumab 1mg/Kg every 6 weeks until disease progression (n=46). Toxicity data favored the latter group with estimates of grade 3 and 4 treatment related adverse events 29, 35, 29 and 28%, respectively. These results indicate that the nivolumab dose of 3mg/Kg administered every 2 weeks combined with ipilimumab 1mg/Kg every 6 weeks until disease progression has favorable disease profile and should be further explored in future clinical trials.

1.2.5 Biomarkers

Significant efforts continue to explore potential tumor cells and microenvironment-related biomarkers that could predict response to nivolumab and other checkpoint inhibitors. For instance, tumor cell expression of PD-L1 was characterized with the use of immunohistochemistry (IHC) staining and pharmacodynamics changes in the peripheral blood absolute lymphocyte count in the study investigating the combination of nivolumab and ipilimumab in melanoma.³² PD-L1 positivity was defined as expression in at least 5% of tumor cells. Among patients treated with the concurrent regimen of nivolumab and

NU Study Number: NU 16N03
BMS Study Number: CA 209-802

ipilimumab, ORs were observed in patients with either PD-L1-positive tumor samples (6 of 13 patients) or PD-L1-negative tumor samples (9 of 22). In the sequenced regimen cohorts, a higher number of overall responses were seen among patients with PD-L1-positive tumor samples (4 of 8 patients) than among patients with PD-L1-negative tumor samples (1 of 13) suggesting the possibility that these tumors have higher response rates to the combination. Other biomarkers such as tissue expression of PDL-2, interferon- γ (IFN- γ), IDO (indoleamine-pyrrole 2,3-dioxygenase), and T cell CD8+ infiltration are also being investigated. However, there is no definitive date to support the use of any of these biomarkers to select patients for treatment at this time.

1.3 Rationale for the Current Study

Monoclonal antibodies immune checkpoint inhibitors have shown evidence of antitumor efficacy among various solid tumors as discussed below. Recent evidence showed significant correlation between higher somatic mutation burden and better immune checkpoint inhibitor response.¹⁷ Frequent mutations in DNA damage repair genes and chromatin remodeling genes and a wide array of somatic alterations found from the recent genomic sequencing studies in ACC may result in a significant number of neoepitope peptides derived from these altered genes, eliciting the generation of specific cytotoxic T cells.^{18,19} Also results from early phase clinical trial support that activation of the immune system through vaccination may indeed results suppression of the adenoid cystic tumor growth.¹¹

1.3.1 Study design

The rationale for use of a phase II study is based on the fact that it allows for evaluation of anti-tumor efficacy of nivolumab combined with ipilimumab in patients with recurrent/metastatic adenoid cystic carcinomas. Patients with non-ACC who also have recurrent/metastatic disease will be studied as part of an exploratory objective but will not be included in our statistical analysis. To our knowledge this is the first study to address this question.

1.3.2 Nivolumab flat dose regimen

The safety and efficacy of 240 mg (monotherapy) Q2W flat dose of nivolumab has recently received FDA approval and is expected to be similar to the 3 mg/kg Q2W dosing regimen. Using the population PK (PPK) model, exposure of nivolumab at 240 mg flat doses is identical to a dose of 3 mg/kg for subjects weighing 80 kg, which is the approximate median body weight in nivolumab clinical trials. Across the various tumor types in the clinical program, nivolumab has been shown to be safe and well tolerated up to a dose level of 10 mg/kg, and the relationship between nivolumab exposure produced by 3 mg/kg and efficacy and safety has been found to be relatively flat. Given the similarity of nivolumab PK across tumor types and the similar exposures predicted following administration of 240 mg flat doses compared to 1mg/kg and 3 mg/kg, it is expected that the safety and efficacy profile of 240 mg nivolumab will be similar to that of 3 mg/kg nivolumab.

In addition, nivolumab 480 mg administered once every 4 weeks (Q4W) is currently under investigation. The less frequent dosing regimen is designed to afford more convenience to the target patient populations. The nivolumab dose of 480 mg Q4W was selected based on clinical data and modeling and simulation approaches using PPK and exposure-response analyses of data from studies in multiple tumor types (melanoma, NSCLC, and RCC) to provide an approximately equivalent dose of nivolumab 3 mg/kg Q2W. Exposures following nivolumab 480 mg Q4W regimen are predicted to be within the exposure ranges observed at doses up to 10 mg/kg Q2W used in the nivolumab clinical program, and are

NU Study Number: NU 16N03
BMS Study Number: CA 209-802

not considered to put participants at increased risk. Hence, the flat doses of 240mg and 480mg nivolumab are under investigation.

1.3.3 Ipilimumab dose regimen

Ipilimumab will be administered at 1mg/Kg every 6 weeks until disease progression in combination with nivolumab 240mg every 2 weeks. As discussed above, this drug combination regimen has been compared with the current FDA approved combination regimen of nivolumab 1mg/Kg every 3 weeks x 4 and ipilimumab 3mg/Kg every 3 weeks x 4 followed by nivolumab 3mg/Kg every 2 weeks until disease progression and showed favorable toxicity profile with maintained efficacy among patients with advanced lung cancer.²³

1.4 Exploratory Studies

In the era of personalized therapy appropriate patient selection to immune-check point inhibitors remains an elusive goal. There are conflicting data on the predictive value of PD-L1 expression on PD-1 directed therapy in solid tumors.^{30,42} Herbst et al. showed that patients with solid tumors including non-small cell lung cancer and melanoma treated with humanized PD-L1 antibody had higher ORR when immunohistochemistry showed intense staining for PD-L1 in the tumor⁴³. The same correlation was not observed on stratified analysis according to tumor cell membrane PD-L1 expression of non-small cell lung cancer patients treated with nivolumab therapy in the second line setting.³⁰

All subjects will be asked to provide consent to supply a sample of their archival tumor blocks if a sample is available. Archival tumor samples, when available, may be evaluated for the immunosuppressive biomarker PD-L1 protein on tumor cells and the expression level and localization of other markers of inflammatory/immune signature that may include but not be limited to PD-1, OX40, CD73, CD39, T cell immunoglobulin and mucin domain containing protein 3 (TIM3), GITRL, CTLA-4, CD3, CD4, CD8, protein tyrosine phosphatase receptor type C (CD45RO), forkhead box P3 (FOXP3), and granzyme by immunohistochemistry analysis and/or flow cytometry and comprehensive genomic profiling.

The association between treatment response and the above biomarker status will be investigated.

2.0 OBJECTIVES & ENDPOINTS

2.1 Primary Objective & Endpoint

To assess median progression-free survival (PFS) as well as PFS at 6 and 12 months in patients with recurrent or metastatic adenoid cystic carcinoma (ACC) treated with a combination of nivolumab and ipilimumab.⁴⁴ Patients will have scans every 12 weeks. Efficacy will be evaluated in all patients who receive at least one dose of study treatment and have had their disease re-evaluated.

2.2 Secondary Objectives & Endpoints

2.2.1 To assess the efficacy of nivolumab and ipilimumab according to response rate (RR), disease control rate (DCR; CR, PR, and SD at 6 and 12 months), overall survival (OS) and progression free survival (PFS) using RECIST criteria in patients with recurrent or metastatic ACC. ⁴⁴

The time in months from start of treatment to progression or death will be measured for all patients who receive at least one dose of study drug. Patients will be followed up to 2 years after completion of treatment. Efficacy will be evaluated in all patients who receive at least one cycle of study treatment.

2.2.2 To assess the efficacy of nivolumab and ipilimumab according to ORR, DCR, PFS, and OS in patients with recurrent or metastatic ACC using irRECIST criteria.⁴⁵ Efficacy will be evaluated in all patients who receive at least one dose of study treatment and have had their disease re-evaluated.

2.2.3 To assess the safety and tolerability profile of nivolumab and ipilimumab therapy in patients with recurrent or metastatic ACC using CTCAE version 4.03. The number, frequency, and severity of adverse events will be collected from time of consent until 30 days after study treatment for all patients who receive at least one dose of study drug.

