4.0 TREATMENT PLAN

4.1 Overview

[figure not shown]
Nivolumab and ipilimumab combination will be administered intravenously until disease progression or intolerable toxicity. Nivolumab will be given at 240mg over 30 minutes (-5 / +15 minutes) every 2 weeks starting with Cycle 1 Day 1 for the first 16 weeks (1 cycle = 12 weeks). Starting with Cycle 2 Day 29, nivolumab will be given at 480mg IV over 60 minutes (-10 / +15 minutes) every 4 weeks. Ipilimumab will be given at 1mg/Kg every 6 weeks starting with Cycle 1 Day 1 over approximately 90 minutes (-5 / +15 minutes). On days when both nivolumab and ipilimumab are administered, nivolumab should be given first, followed by ipilimumab about 30 minutes after completion of nivolumab. Patients will be assessed for response every 12 weeks (± 7 days). Note: Please refer to section 4.4 for patients who may continue treatment after initial progression.

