6.4 Definitions

Evaluable for toxicity. All patients will be evaluable for toxicity from the time of their first treatment with nivolumab and or ipilimumab.

Evaluable for objective response. Only those patients who have received at least one dose of therapy, and have had their disease re-evaluated will be considered evaluable for response. These patients will have their response classified according to the definitions stated below.

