6.8 Evaluable patients

All patients who receive at least one dose of nivolumab will be considered evaluable for the toxicity endpoints.

All patients who receive at least one dose of nivolumab and have a radiologic evaluation of disease are evaluable for efficacy endpoints.

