10.3 Data Analyses Plans

Response rates and 95% confidence intervals will be calculated using exact binomial probability distributions for discrete outcomes. Progression-free survival and overall survival will be graphically depicted using Kaplan-Meier curves. Adverse events will be summarized descriptively using frequencies and percentages. Statistics will be given on type, severity, frequency and attribution of adverse events. Sample size considerations are described above.

An intention to treat analysis will be done. In a single group Phase II study, intention to treat means that all patients who are evaluated and registered for the study are followed and analyzed regardless of (a) whether they were subsequently found to be protocol ineligible and (b) the amount of study treatment (nivolumab/ipilimumab) they received. To calculate progression-free and overall survival in patients who received nivolumab/ipilimumab, times will be taken from the time of study registration. This definition parallels the definition of intention to treat in randomized clinical trials.

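### The plan names three conflicting populations for the secondary response and disease control rates; the one-cycle rule in 2.2.1, if followed, probably raises the RECIST rates and makes them non-comparable with irRECIST

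*Combined protocol and SAP*

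**What the plan says.** The secondary response rate (RR) and disease control rate (DCR, also called CBR) in ACC are to be reported under RECIST and again under irRECIST. Section 10.3 plans exact binomial 95% intervals for response rates. The population is stated in several places:

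- **2.2.1 (RECIST: RR, DCR, OS, PFS):** "Efficacy will be evaluated in all patients who receive at least one cycle of study treatment". Section 4.1 gives the length: "1 cycle = 12 weeks". For the time-to-event measures the same paragraph uses a wider set: "The time in months from start of treatment to progression or death will be measured for all patients who receive at least one dose".
- **2.2.2 (irRECIST: ORR, DCR, PFS, OS):** "Efficacy will be evaluated in all patients who receive at least one dose of study treatment and have had their disease re-evaluated".
- **6.4 (who is evaluable):** "Only those patients who have received at least one dose of therapy, and have had their disease re-evaluated will be considered evaluable for response".
- **6.8 (all efficacy endpoints):** "All patients who receive at least one dose of nivolumab and have a radiologic evaluation of disease are evaluable for efficacy endpoints".
- **10.3 (analysis plan):** an intention-to-treat analysis in which "all patients who are evaluated and registered for the study are followed and analyzed", regardless of "the amount of study treatment (nivolumab/ipilimumab) they received".

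Two further provisions decide who is affected. Footnote 4 to the Section 5.0 table allows scans earlier than the 12-weekly schedule. Section 4.8 keeps imaging patients who stop for toxicity without progression, and counts a radiographic response seen afterwards in the final analysis.

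**The concern.** Receiving a 12-week cycle is something that happens after treatment starts. It depends on not progressing, not dying and tolerating the drugs, so a denominator defined by it is selected partly on outcome. A patient who progresses on a scan at week 8 and stops is a documented failure. That patient is evaluable under 6.4, 6.8 and 2.2.2 but absent from the RECIST rate under 2.2.1.

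Two results are at stake. The RECIST RR and DCR, with their exact intervals, may be reported too high. The comparison of RECIST with irRECIST also loses its meaning, because part of any difference would come from the denominators and not from the criteria. And since no order of precedence is given, the choice among the three populations could be made after the data are seen.

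**Working it through.** **Plan's own figure.** There is none to reproduce. The documents give no early-dropout rate and no expected DCR by population. The only fixed input is 43 ACC patients (Section 10.2).

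**Step 1: who falls in which set.** Take *receives one cycle* in its natural sense, that is, 12 weeks of treatment. Routine re-evaluation starts at Cycle 2 Day 1 (Section 5.0, footnote 3), so a patient who stops sooner has a re-evaluation only through an early discretionary scan or through imaging after stopping.

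| Patient who stops in cycle 1 | 2.2.1 | 2.2.2, 6.4, 6.8 | 10.3 |
|---|---|---|---|
| Progression on an early scan | out | in, failure | in |
| Toxicity stop, later imaged under 4.8 | out | in, by scan result | in |
| Death or decline before any scan | out | out | in |

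The third row shows that the one-dose-plus-re-evaluation rule also loses early failures, though fewer of them.

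**Step 2: size against all 43.** Let x be the number controlled, k the number of early leavers, none of them controlled. The rate moves from x/43 to x/(43 − k). Assume k = 4 to 11 (4/43 = 9.3%; 11/43 = 25.6%) and x = 19:

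- all kept: 19/43 = 44.2% (exact 95% CI 29.1 to 60.1)
- k = 4: 19/39 = 48.7%, up 4.5 points
- k = 11: 19/32 = 59.4% (40.6 to 76.3), up 15.2 points

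**Step 3: size against the re-evaluated set.** This is the direct contrast between 2.2.1 and 2.2.2. Leavers without a scan are missing from both sets, so only re-scanned leavers, m of the k, make a difference: x/(43 − k + m) against x/(43 − k). With about half re-scanned and x = 19:

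- k = 4, m = 2: 19/41 = 46.3% against 19/39 = 48.7%, a gap of 2.4 points
- k = 11, m = 5: 19/37 = 51.4% against 19/32 = 59.4%, a gap of 8.0 points

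**Step 4: direction.** Dropping k leavers, c of whom are controlled, raises the rate only if c/k is below the rate among those who stay. For k = 11 the break-even is 11 × 19/32 = 6.5. With c = 6 the full rate is 25/43 = 58.1%, still below 59.4%; with c = 7 it is 26/43 = 60.5%, above it. For k = 4 the break-even is 4 × 19/39 = 1.9, so two controlled leavers out of four are enough to cancel the bias (21/43 = 48.8% against 48.7%).

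**The case against.** Much of the case on the other side stands.

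- **The plan does not settle on the one-cycle rule.** A reader might infer that RECIST response is evaluated only in patients who complete a cycle. Sections 6.4, 6.8 and 10.3 say otherwise, so early failures may never be dropped. This changes the finding from a fixed bias to a contradiction. It does not remove it, because 2.2.1 is the text of the objective itself and nothing ranks it below the others.
- **The text says receive, not complete, and does not define it.** If starting a cycle were enough, the exclusion would almost vanish. Against that reading, the same paragraph uses one dose for the time-to-event measures, and the change of unit would then have no purpose. A denominator open to two readings needs correcting in any case.
- **Early stopping is not automatically failure.** A toxicity stop with stable disease or a response on a scan is not a RECIST failure, and 4.8 counts a later response. Upward bias is therefore probable, not certain, as Step 4 shows.
- **The larger figures need strong assumptions.** The 15-point rise needs about 25% early loss, no disease control among the leavers, and a comparison with all 43. A reader might set it beside the design's 45% to 65% difference and conclude that the trial's decision is at risk. The documents do not support that. The decision is a count, with 24 or fewer of 43 leading to rejection (10.2), and the primary PFS set in 2.1 and 6.2 does not use the one-cycle sentence.

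**Conclusion.** The point holds as an unresolved contradiction over the population for the secondary RR and DCR/CBR: one cycle in 2.2.1, one dose plus re-evaluation in 2.2.2, 6.4 and 6.8, and intention to treat in 10.3. Following 2.2.1 would probably bias the RECIST rates upward and would make them non-comparable with irRECIST.

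With 19 controlled, the illustrated effect on DCR is about 2 to 8 points against the re-evaluated set and about 4 to 15 points against all 43. These sizes rest on assumed early-loss counts of 4 to 11, leavers taken as not controlled and, for the smaller range, about half of them re-scanned. None of these inputs is in the documents. The primary endpoint and the go/no-go count are not affected by this sentence. It should be corrected before analysis, but it does not threaten the design.

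**What to change.** 1. Delete the one-cycle sentence in 2.2.1.
2. Name one denominator for RR and DCR/CBR under both RECIST and irRECIST, consistent with the intention-to-treat statement in 10.3, and align 2.2.2, 6.4 and 6.8 with it. State at the same time whether patients who are registered but never treated, whom 4.10 allows to be replaced, are counted.
3. Classify each patient by documented assessments, including those made after early stopping, as 4.8 provides. Do not count every early stopper as a failure, because that would override 4.8.
4. Count patients with no usable post-baseline assessment as not responding and not controlled.
5. Show any evaluable-set or one-cycle rate only as a labelled supportive figure, with its denominator.

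The cost is a wording change in the population statements and one derivation rule. No patient, visit or scan is added. The reported RR and DCR may be slightly less favourable.
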